1.3.3.2. Potential risks of Niacin (active-placebo-control agent)

A participant's symptoms of depression or burnout could change or perhaps worsen during the course of the study, as symptoms might change if that individual were not participating in the study. However, there is no reason to believe that niacin &an active-placebo-control would exacerbate symptoms of depression or burnout. Niacin has expected physiological side effects that make it well suited to be used as an active placebo, including flushing, tingling, itching, and redness of the face, arms, and chest, as well as headaches, and these are documented to be transient. Other minor, transient, and occasional side effects include upset stomach, intestinal gas, and dizziness. Participants will be informed about these potential side effects, and they will be monitored throughout the drug administration visits.

1.3.3.3. Potential risks of changes or delay in participant treatments being received prior to screening

Participants will be asked to refrain from starting new medications, including OTC supplements, during the procedures involved in this study. Should circumstances warrant a change in treatment, then participants will be asked to immediately notify the study team. If medically warranted, the participant begins to experience a decline, or their provider believes a treatment change is necessary, then the participant will be withdrawn from the study and encouraged to seek treatment.

For participants who are tapering and discontinuing antidepressant medications prior to entering the study, the following safety measures will be taken:

- Participants will be required to discuss changes in their antidepressant medication with their own prescribing provider, and to provide the study staff with a written note from the provider describing the plan.
- Study staff will be in contact with a participant who is tapering their antidepressant medication weekly with a phone safety assessment that will involve use of the C-SSRS. (These safety assessments are not designated as a 'study visit' so do not appear in the study visit flowsheets in Section 3.1 that summarize research procedures).
- Participants will be required to provide the name of at least one adult who will be in continuous contact with them during the taper and discontinuation period.

1.3.3.4. Risk of Emotional Responses, Discomforts During Administration & follow-up meetings.

During preparation, medication dosing, and integration sessions, participants will be asked to think about and to discuss their thoughts and emotions about their experiences working in the COVID pandemic, including the impact that these experiences have had on their lives. They may experience emotional responses to speaking about these thoughts, feelings, and concerns. The medication dosing session will take place at Harborview Medical Center and will be staffed by two investigators. The PI and/or investigators who will be present during the drug session will meet the patient at least 3 times prior to the medication dosing session. This will be done as part of psychoeducation that provides the participant with expectations for what to expect during the sessions.

Page 10 Version 1.16, July 18, 2022

1.3.3.5. Risks from routine medical evaluations.

The other risks involved in this research are generally considered minimal and include those normally associated with clinical care or research such as psychiatric evaluations, medical examinations, lab work - urine drug screening, blood draws, and research questionnaires.

Psychiatric Evaluations. Participants must answer personal questions, which may feel unpleasant or tiring, or may find discussing their symptoms andtheir illness during the psychiatric evaluation unpleasant or upsetting. Screening is necessary to assess participant eligibility. The major disadvantages of these assessments are the time that it takes to complete them. These clinical and research methods represent minimum risk(s).

Blood draws and urine tests for routine screening, including pregnancy testing. Participants will undergo a blood draw for a comprehensive metabolic panel, pregnancy test, liver panel. These tests prior to the psilocybin session allow the investigators to ensure that there are no contraindications to subjects' participation in the study, such as liver function abnormalities which could produce higher than expected levels of psilocybin. Higher levels of psilocybin may produce prolonged duration or greater intensity of subjective effects. Weighing the risks and benefits of a blood draw versus potentially unpredictable levels of psilocybin, the liver panel conveys more benefits than risks. Serum pregnancy and / or urinary pregnancy testing will be conducted at the screening visit to avoid the risk of unintended psilocybin exposure in utero. Less than 50mL will be drawn per collection. There will be a single blood draw over the course of study. The blood draw may produce temporary discomfort as a result of sampling blood, and discomfort or bruising at the blood drawing site. The urinary drug screen is necessary to verify abstinence from illicit substances or nonprescription stimulants prior to the psilocybin session.

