Following the investigator brochure, although there have been no reports of their use in well-reported clinical trials with oral psilocybin, medications will be available for the treatment of causal symptomatic hypertension, agitation, or severe psychosis. Typically, these supplies are two dosage unitsof labetalol, nitroglycerin, lorazepam and/or diazepam, and risperidone or similar orally- disintegrating antipsychotic.

If any participant presents with an adverse reaction to the psychopharmacological agent as reported by them or assessed by a member of the research team, we will discontinue the study and call for medical assistance. Finally, the participant may be withdrawn from the study if his/her withdrawal is in the best interests of either the participant or of the research (e.g., due to a medical condition making the procedures unsafe or any condition making interpretation of the results difficult).

Niacin: (active-placebo-control agent): There is no reason to believe that niacin would exacerbate symptoms of depression or burnout or PTSD. Participants will be informed about Niacin's potential side effects, and they will be monitored throughout the drug administration visits. The rationale for using an active-placebo-control agent rather than active low dose of psilocybin (ranging 2mg -4mg), which have been used in the recent palliative care studies is because a partial response has been reported even with these low doses.

Page 14 Version 1.16, July 18, 2022

Changes or delays in treatments being received prior to screening: Participants will be asked to refrain from starting new medications to allow the participant and this study to safely proceed. If medically warranted, or the participant begins to experience a decline, or their provider believes a treatment change is necessary, then the participant will be withdrawn from the study and encouraged to seek treatment.

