4.1. Inclusion Criteria

- a. Participants must be physicians or nurses or advance practice providers (nurse practitioners or physician assistants) with at least 1 month of frontline clinical experience during the COVID pandemic who rate at least 2 of 4 items from the COVID Exposure index as 'more than half the days' during their peak 2 week period of exposure:
 - i. Caring for someone critically ill with COVID-19, or who became critically ill while you were involved.
 - ii. Working longer hours than usual in order to provide assistance or care to individuals with COVID-19
 - iii. Witnessing or responding to a death related to COVID-19, or losing a patient you had been caring for to COVID-19
 - iv. Caring for patients who have died without family physically present due to COVID-19 precautions

- b. Have a Montgomery-Asberg clinician-administered depression score \geq 21, indicating moderately severe symptoms. This measurement is clinician-administered and will be performed by a study team member who is not a therapist, who will receive special training.
- c. Have had persistent symptoms despite at least one medication and/or therapy trial of standard care treatment for depression.
- d. English speaking able to understand the process of consent and the risk and benefits associated with the study, and able to give written informed consent.
- e. Must be willing to sign a medical release for the investigators to communicate directly with their therapist and doctors to confirm a medication and/or medical history. This is decided on a case by case basisupon the discretion of the PI.
- f. Must be driven home after the medication dosing session by a driver(which could be a friend, family, rideshare or taxi).
- g. Must provide at least one adult to have continuous contact with the participant, provide participant transportation, monitor changes in the participant's behavior, and notify research staff of behavior changes.
- h. Has been off selective serotonin inhibitors for five half-lives of the drug plus 2 weeks.
- i. Must avoid taking any psychiatric medications or starting a new psychiatric medication during the study. Should participant's doctor recommend starting a new psychiatric medication, participant will be required to notify the study team and the subject would withdraw from the study

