- j. Must provide a contact (relative, spouse, close friend, or other caregiver) who is willing and able to be reached by the Clinical Investigators in the event of a participant becoming suicidal.
- k. Must have a negative pregnancy test at study entry and prior to each medication dosing session if able to bear children and must agree to use adequate birth control.
- Are willing to commit to preparation sessions, medication dosing sessions, integration sessions, to complete evaluation instruments and commit to be contacted for all necessary telephone contacts.

4.2. Exclusion Criteria.

- a. Personal or immediate family history of schizophrenia, bipolar affective disorder, delusion disorder, paranoid disorder, or schizoaffective disorder.
- b. Suicidal ideation with a C-SSRS > 3
- c. Current substance abuse disorder (except in the case of mild alcohol use)
- d. Neuroleptic and SSRI medications that cannot be tapered and discontinued in conjunction with the participant's prescribing physician.
- e. Unstable neurological or medical condition; history of seizure, chronic/severe headaches.
- f. Positive urine pregnancy test at the time of screening
- g. Any unstable medical condition that my render study procedures unsafe based on the medical history performed as part of the screening procedures, including active cardiac medical issues such as ongoing angina, uncontrolled hypertension, or recent cardiac ischemia requiring medical attention (within the past 3 months
- h. Any use of psychedelic drugs within the prior 12 months.
- i. Use of tramadol, due to the potential for serotonin syndrome with concomitant use of

Page 23 Version 1.16, July 18, 2022

psilocybin.

- j. Allergy to niacin (N.B. the investigators will inform participants that flushing, redness, tingling, and headache are normal side effects that do not predict anaphylaxis, which although reported is extremely rare).
- k. Individuals who are on MOAI (monoamine oxidase inhibitors) or who have a known sensitivity to the drug or its metabolites. Psilocybin is contraindicated in medications that are known UGT (UDP-glucuronosyltransferase) enzymemodulators. The concurrent use of SSRI/SNRI meds is assumed to be contraindicated due to the potential to increase the risk of serotonin syndrome and/or to attenuate the binding of psilocin to the HT2A receptor.

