4.5. Participant Withdrawal or Termination

Participants may withdraw their consent for use of their data and/or terminate participation in the study at any moment during the study by calling the Principal Investigator or a member of the research team. To revoke authorization of the use and disclosure of Personal Health Information, the participant must follow-up the phone call by submitting a request in writing to the Principal Investigator. In this event, the Principal Investigator will indicate in the data base that consent from the participant is no longer active, and that data can no longer be used.

Page 24 Version 1.16, July 18, 2022

A participant may be withdrawn from the research for any of the following reasons:

- (1) A participant will be withdrawn if they become actively suicidal
- (2) A participant will be withdrawn if during the preparation visits, they show signs of severe personality disorder that was not evident in the screening visit.
- (3) A participant may be withdrawn if their withdrawal is in the best interests of either the participant or of the research (e.g., due to a medical condition making the procedures unsafe or any condition making interpretation of the results difficult).
- (4) A participant may be withdrawn if they are unable to comply with study visits (e.g., they miss their preparation visits without explanation).

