	Assessment for discharge home.

At about the same time of each heart rate/blood pressure measurement, monitors will complete notations in the Medication Day Case Report Form to rate the presence and intensity of behaviors, signs, and reported symptoms, including sleepiness, amount of speech, anxiety, stimulation/arousal,

tearing/crying, nausea/vomiting, yawning, restlessness, feelings of unreality, visual changes, euphoria, and peacefulness. Video and audio recordings will be made throughout the session, as allowed by participants.

Participants will be encouraged to lie comfortably in bed wearing eye shades during the first few hours of the experience and to listen to pre-selected music chosen by the study staff. Two team members will remain with the participants the entire time and beavailable for any processing of intrapsychic material made manifest by the treatment.

If participants experience or report on any adverse effects or if the research staff feelsthat at the end of testing, that the participant has any adverse effects, participants will be asked / required to remain until effects wear off and medically cleared by the PI. Medical assistance will be offered. The investigators will query participants about suicidal ideation or intent during screening, and prior to each psilocybin session. Participants who evidence suicidal ideation or intent will be withdrawn from the study and referred to appropriate psychiatric care.

In the event that participants experience distressing anxious symptoms during the drug session, the clinical personnel in attendance (the principal investigator and team member) will initiate verbal communication designed to reorient and reassure that participant. The occurrence and intensity of anxiety or panic responses can be reduced through providing participants with information on potential drug effects, supervision, and monitoring of participants for the duration of drug effects. The goal in this study is to treat participants undergoing anxiety or panic reactions first by verbal and psychological interventions and using anxiolytic medication only after verbal and psychological interventions have failed, and if participants are endangering themselves or others. Residual symptoms will be addressed during the frequent follow-up psychotherapy visits with the investigators.

At the end of the medication dosing session:

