If participants experience or report on any adverse effects or if the research staff feels that at the end of testing, that the participant has any adverse effects, participants will be able to remain until effects wear off (likely only for a short period) and medical assistance will be offered. Participants will be free to withdraw from the study whenever they wish. In addition, if any participant presents with an adverse reaction to the psychopharmacological agent as reported by them or assessed by a member of the research team, we will discontinue the study and call for medical assistance

6.5. Safety Plan for Suicidality:

During all study visits a study investigator with clinical training will assess the participant's well-being – responses, intent, plan, etc. while administering the C-SSRS (Columbia Suicidality Severity Response Scale). If these procedures result in any serious concerns on the part of the investigator, they will either ask the participant to meet with or call the PI or escort the participant to the

Page 31 Version 1.16, July 18, 2022

emergency room. If necessary, they will also call the participant's treating clinician and/or their emergency contact. As part of the consent, participants are required to designate an emergency contact person and provide their treating clinician's contact information. We will ask the treating clinician for their local plan for such emergencies so the study team can follow this plan should an emergency situation arise.

7. Payments for Participation (Economic Considerations)

Participants will not be paid for their participation. Expenses of participating in the study, such as parking will be covered by the study.

8. Assessment of Safety

- 8.1. Specification of Safety Parameters
- 8.1.1. Definition of Adverse Events (AE)

Adverse events (AEs) are defined any untoward, physical, social, economic, or psychological occurrence affecting human subjects in research. An AE can be any unfavorable or unintended event including abnormal laboratory finding, symptom, reaction, or disease. An AE does not necessarily have a causal relationship with the research, or any risk associated with the research, the research intervention, or the assessment. Adverse events involve subjects only.

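### Withdrawal for decline, treatment change or active suicidality has no Day-28 MADRS rule and no missing-data method, so the intent-to-treat analysis can become a completer analysis

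*Combined protocol and SAP*

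**What the plan says.** **Withdrawal rules.** Section 1.3.3.3 removes a participant when "the participant begins to experience a decline, or their provider believes a treatment change is necessary, then the participant will be withdrawn from the study". Its heading refers to treatments received before screening, but its text covers the whole period of study procedures. Section 1.3.3.8 repeats the triggers, "If medically warranted, or the participant begins to experience a decline, or their provider believes a treatment change is necessary", with the same consequence. Under section 4.1(i), if a doctor recommends a new psychiatric medication, the "participant will be required to notify the study team and the subject would withdraw from the study". Section 4.5(1) adds: "A participant will be withdrawn if they become actively suicidal". None of these is limited to the time before randomisation.

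**Data after withdrawal.** Section 4.5 bars use of data only when consent is revoked; the investigator then records that "consent from the participant is no longer active, and that data can no longer be used". It does not say whether someone withdrawn for another reason is still rated.

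**Analysis.** Section 9.2 compares mean MADRS change at 4 weeks by a two-sample t-test, or a Wilcoxon rank-sum test if assumptions fail. It states the intent-to-treat principle in one sentence. It assumes 15% dropout and enrols 36 so that 30 complete. It gives no analysis set, imputation, repeated-measures model or missing-data sensitivity analysis. The section 3.1 schedule collects the MADRS on Days 1 and 8, but those ratings have no stated role in the primary analysis.

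**The concern.** Getting worse, or needing new treatment for depression, is the primary outcome or close to it. If those events end participation and no Day-28 score is taken, scores go missing because of what they would have been. Intent-to-treat then has nothing to work with for those people unless a handling rule exists, and none is given.

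The setting makes this plausible. Section 3.1.4 keeps participants off antidepressants until the Day-28 measures, and section 1.3.3.2 accepts that symptoms could worsen during the study. With 15 per arm, one person is 1/15, about 7%, of an arm. Enrolling extra people restores the number analysed but not the composition of the arms. A method chosen after unblinding would also be open to challenge.

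**Working it through.** **1. The plan's own figures reproduce.** Inputs from section 9.2: two-sided 0.05, 15 per arm, effects of 1.06 and 1.23 SD. Noncentral t with 28 df and noncentrality d × √(n/2):
- 1.06 × √7.5 = 2.90, power 80%
- 1.23 × √7.5 = 3.37, power 90%
- Enrolment: 30 / 0.85 = 35.3, rounded up to 36; 36 − 30 = 6 non-completers

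The arithmetic is sound. Section 9.2 also says that 30 will be randomised, so it is unclear how many of the 6 losses follow randomisation. If 30 are randomised and 15% are then lost at random (about 13 per arm), power is about 74% at 1.06 SD and 85% at 1.23 SD.

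**2. Search for a Day-28 rule after withdrawal.**
- The footnote to the section 3.1 schedule has the coordinator verify Day-28 measures, but only as a condition for unblinding.
- Section 6.1 keeps raters blind if the code is broken for an emergency. It does not say that a withdrawn participant is rated.
- Section 8.2 continues weekly adverse-event review to 4 weeks. It does not mention the MADRS.
- Section 4.5 permits ratings after withdrawal without revoked consent, but does not plan them.

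**3. Illustration.** The documents give no rate or pattern of loss, so everything here about loss is assumed. There are 15 per arm, normal change scores with SD 1 (higher is better), and a t-test on those remaining. The loss score is 0.5 × outcome + √0.75 × independent noise, and the lowest scores are lost.

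Loss from one arm only can be checked by hand. The three lowest of 15 standard normal values average −1.736, −1.248 and −0.948. Losing k people shifts that arm's mean by 0.5 × (sum of the k absolute values) / (15 − k):
- k = 2: 0.5 × 2.984 / 13 = 0.115
- k = 3: 0.5 × 3.932 / 12 = 0.164

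So 1.06 becomes 1.175 or 1.224 if psilocybin participants are lost, and 0.945 or 0.896 if niacin participants are lost. Simulation with 100,000 replicates agrees within 0.01.

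| Assumed loss | Estimate if true effect is 1.06 SD | Power | Type I error if no effect |
|---|---|---|---|
| None | 1.06 | 80% | 5% |
| 2–4 at random | 1.06 | 77–73% | 5% |
| 2–4, one rule for both arms, correlation 0.5 | 1.01–0.98 | 75–70% | 5% |
| 2–3, psilocybin only, correlation 0.5 | 1.18–1.23 | – | 6–7% |
| 2–3, niacin only, correlation 0.5 | 0.95–0.90 | – | 6–7% |
| 2–4 worst outcomes, one rule (extreme bound) | 0.88–0.77 | 69–59% | 5% |

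The third row depends on the loss score carrying only half the arm difference. If loss follows a Day-8 score that carries the full 1.06 SD effect (correlation 0.5, 4 lost), completers give about 0.91 SD and 62% power. The 5% under a common rule needs the same distribution in both arms throughout. If an early 1.06 SD effect has faded by Day 28 and loss follows the early score, type I error is 5.7 to 6.5%, mostly against psilocybin.

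**The case against.** The strongest reply is that the loss is hypothetical. The risk table in section 1.3.3.8 says worsening has not been reported in published studies since 2000. The open-label offer gives participants a reason to stay. Consent and the preparation visits precede randomisation, so some or most of the six planned losses may fall before it, where they do not touch intent-to-treat. Under one common rule at correlation 0.5 the bias is small and conservative, costing about 2 to 4 power points beyond random loss. All of this stands, and it limits the weight of the point. It does not supply the missing rule.

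A reader might infer more than the documents support:
- **That withdrawn participants are excluded.** No section says so. What is absent is how they enter the analysis.
- **That the named tests rule out intent-to-treat.** They do not; either could follow imputation.
- **That the trial is tilted towards psilocybin.** Losing poor niacin outcomes understates a benefit; losing poor psilocybin outcomes overstates it. Nothing shows which is likelier.
- **That the rule in section 6.2.3, "Participants who evidence suicidal ideation or intent will be withdrawn from the study", is a main source of loss.** The query comes at screening and before dosing, so it cannot reflect response to the drug. The section 3.1 schedule randomises on the dosing day, leaving little or no window after randomisation; section 6.2.1 puts randomisation at the end of visit 2.
- **That the adverse-reaction wording in section 6.4, "we will discontinue the study and call for medical assistance", belongs here.** It may mean only stopping that participant's procedures, and nothing in this point rests on it.

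**Conclusion.** The point holds as a gap in the plan. Sections 1.3.3.3, 1.3.3.8, 4.1(i) and 4.5(1), followed as written, can remove people for reasons close to the outcome, and neither 4.5 nor 9.2 says how they are rated or analysed. It should be fixed before unblinded data are analysed.

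The amount and direction of bias cannot be stated from the documents. The figures above show only what a few such losses could do at this sample size; the counts, the correlation and the split by arm are assumptions. The common-rule cases at correlation 0.5 are modest, and the larger shifts need loss concentrated in one arm or among the worst outcomes.

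A separate inconsistency affects who would be withdrawn. Section 4.5(1) refers to active suicidality, section 6.2.3 to ideation or intent, and the exclusion in section 4.2(b) reads "Suicidal ideation with a C-SSRS > 3". The sponsor must reconcile these; this review takes no view on which threshold is right.

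**What to change.** **Section 4.5.** State that stopping study procedures is separate from leaving follow-up. Every randomised participant who has not withdrawn consent should have the Day-28 MADRS from the existing blinded rater, remotely if needed, with any new treatment recorded.

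**Section 9.2.** State that all randomised participants are analysed. Handle any Day-28 score still missing by one prespecified method that uses the Day 1 and Day 8 MADRS: a likelihood-based repeated-measures model or multiple imputation. Add one sensitivity analysis giving those withdrawn for worsening a prespecified unfavourable value, such as no improvement from baseline.

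The Day-28 rating matters most. With 4 lost and a Day 8 to Day 28 correlation of 0.5 to 0.7, imputation from Day 8 restores the estimate from 0.91–0.84 to 1.06–1.05 SD when loss follows the Day-8 score. When loss follows the unseen Day-28 score, it recovers only 0.84–0.89 SD against about 0.77 SD for completers.

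**Reconcile** sections 4.5(1), 6.2.3 and 4.2(b) on suicidality, with the clinical criteria left to the sponsor.

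**Cost.** Some wording and a few extra ratings. Scores taken after new treatment carry a treatment-policy interpretation, which section 9.2 should say.
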